1.2 Specific Aims/Objectives

#1 (Feasibility; Primary Aim): To determine the feasibility and acceptability of the PATH intervention in patients with hematologic malignancy undergoing HSCT.

PROTOCOL TITLE: Randomized Trial of a Positive Psychology Intervention for Patients with Hematologic Malignancies Undergoing Hematopoietic Stem Cell Transplantation

Hypothesis: The PATH intervention will be deemed feasible with >75% of participants randomized to the intervention arm completing ≥ 6/9 positive psychology exercises. The PATH intervention will be deemed acceptable with mean ease and utility scores of each exercise being ≥ 7/10.

#2 (Effects on Patient-Reported Outcomes): To assess the preliminary efficacy of the PATH intervention on psychological (e.g., depression, anxiety, optimism, positive affect), QOL, and functional outcomes compared to the usual care condition.

Hypothesis: Patients randomized to the PATH intervention will have improved PPWB (e.g., optimism, positive affect, gratitude), mood (e.g., depression and anxiety), and QOL compared to those in the usual care condition.

#3 (Effects on Health Behaviors): To examine the impact of the PATH intervention on behavioral outcomes (e.g., medication adherence, physical activity) compared to those in the usual care condition.

Hypothesis: Patients randomized to the PATH intervention will have improved behavioral outcomes (e.g., medication adherence, physical activity) compared to those in the usual care condition.

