8.0 Study Endpoints*

Primary Endpoint:

- Establish feasibility and acceptability of the PATH intervention in the intervention group.

Secondary Endpoints:

- Compare patients' QOL (FACT-BMT) scores longitudinally between the study groups
- Compare patients' positive psychological wellbeing factors [e.g., optimism (LOT-R) and positive affect (PANAS)] between the study groups
- Compare patients' symptoms of anxiety and depression (HADS) between the study groups
- Compare patients' post-traumatic stress symptoms (PCL-C) between the study groups
- Compare patients' fatigue (PROMIS-fatigue) scores between the study groups
- Compare patients' physical activity (Actigraph GT3X+ data) and physical functioning (PROMIS-PF-20) between the study groups
- Compare patients' medication adherence (MEMS Cap data, SSEQ, MARS-5) between the study groups
- There are currently no anticipated primary or secondary safety endpoints.

Exploratory Endpoints:

- Compare patients' coping (Brief Cope) between the study groups
- Assess whether group differences in patient reported QOL are mediated by improved mood (mediator: HADS) or coping (mediator: Brief Cope)

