10.0 Data and Specimen Banking: Not Applicable

10.1. *Data analysis*

Specific Aim 1 (Feasibility; Primary Aim): To demonstrate the feasibility of the PATH intervention in patients with hematologic malignancy undergoing HSCT: Based on prior work, we define feasibility as >75% of enrolled participants who start the intervention completing at least 6 of the

PROTOCOL TITLE: Randomized Trial of a Positive Psychology Intervention for Patients with Hematologic Malignancies Undergoing Hematopoietic Stem Cell Transplantation

9 PP sessions, consistent with metrics used in prior positive psychology feasibility trials^{17, 54} and other behavioral intervention studies.⁸⁵⁻⁸⁷ We will estimate the feasibility using the proportion who meet the criteria, and we will place an exact 95% binomial confidence interval around the proportion. We will assess acceptability using weekly ratings of ease and utility of each exercise (0=very difficult/not helpful; 10=very easy/very helpful). The mean ease and utility of each exercise and overall will be calculated, and will use a threshold of a mean combined score of 7.0/10 for acceptability that was used in prior studies.^{19,57}

Specific Aim 2 (Effects on Patient-Reported Outcomes): To assess the preliminary efficacy of the PATH intervention on psychological (e.g., depression, anxiety, optimism, positive affect), QOL, and functional outcomes compared to the usual care condition: Analyses will begin with descriptive and graphical summaries of the endpoints and evaluation of whether a normality assumption is reasonable for the endpoint or whether transformation is necessary. We will use a Bonferroni correction to address multiple measures and testing. All statistical tests will be two-sided with a liberal alpha level of 0.2 to detect a signal on the impact of the intervention on patient- reported outcomes. We will summarize participants' baseline characteristics using descriptive statistics (e.g., mean) for continuous variables and proportions for categorical variables.

To examine the immediate impact of the intervention on happiness and optimism, we will use generalized estimating equations (GEE) to determine the immediate impact of a PP session on optimism and happiness. The GEE model will allow us to account for the repeated observations on subjects from the different exercises.

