Based on prior trials in this population,⁹² we anticipate 15% of enrolled participants will be unable to complete the intervention due to medical complications and mortality. Hence, we will enroll 70 participants (35 in the [PATH] PP arm) to target having at least 30 PP participants who complete the intervention. For our primary aim (feasibility), in prior trials, approximately 80% of participants have completed 6 of 9 PP exercises.⁹ Using the same rate, with 30 PATH participants, we will have 95% power (two-sided $\alpha = .05$, binomial proportion test) to demonstrate that the proportion who complete > 6 of 9 PP sessions is larger than 50% (i.e., a majority). For acceptability, using this sample size, we will have 95% power to detect a true mean score of > 7.0 based on prior work (in which mean utility scores were 7.8 ± 1.8).¹² This pilot RCT is not designed to definitively detect significant ($p < .05$) group differences in psychological, QOL, or behavioral outcomes (and we would need between-group effect size differences of $d = .74$ to be powered at 80% to detect significant differences). However, this sample of 30 completers in each group will allow us to preliminarily explore the impact of PATH on clinical outcomes and make tentative estimations of effect sizes.

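### The 95% power stated for acceptability does not follow from 7.8 ± 1.8 against 7.0 with 30 participants, and sections 1.2 and 10.1 give different acceptability rules

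*Combined protocol and SAP*

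**What the plan says.** Section 8.0 makes acceptability part of the primary endpoint: "Establish feasibility and acceptability of the PATH intervention in the intervention group".

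Section 10.2 gives the power statement: "For acceptability, using this sample size, we will have 95% power to detect a true mean score of > 7.0 based on prior work". The prior work is summarised in the same sentence as "mean utility scores were 7.8 ± 1.8". The sample referred to is the 30 PATH participants expected to complete, out of 35 enrolled in that arm. The preceding sentence, on feasibility, names a binomial test at two-sided alpha 0.05. The acceptability sentence names no test, alpha or sidedness, and does not say whether 1.8 is a standard deviation between participants or between single ratings.

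The decision rule appears twice:

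- Section 1.2 requires "mean ease and utility scores of each exercise being ≥ 7/10".
- Section 10.1 (Aim 1) calculates means for each exercise and overall, and then "will use a threshold of a mean combined score of 7.0/10 for acceptability".

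Section 10.1 gives no test or interval for acceptability. Its only Aim 1 interval concerns feasibility: "we will place an exact 95% binomial confidence interval around the proportion". For Aim 2 it adds: "All statistical tests will be two-sided with a liberal alpha level of 0.2".

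**The concern.** A mean of 7.8 lies 0.8 above the threshold, which is less than half of a standard deviation of 1.8. Thirty observations do not normally give 95% power for an effect of that size, so the figure needed checking. The reader is told that the sample is nearly certain to establish one component of the primary endpoint, and the inputs printed beside that statement do not appear to support it.

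The second problem bears on the conclusion itself. A rule that every exercise must satisfy is stricter than a rule on one combined mean. With both in the text, the verdict on acceptability could depend on which section is applied once the ratings are known.

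**Working it through.** **Inputs**

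| Input | Value | Source |
|---|---|---|
| Assumed true mean | 7.8 (utility only) | 10.2 |
| Reference value | 7.0 | 10.1, 10.2 |
| SD | 1.8, unit not stated | 10.2 |
| n | 30 completers; 35 enrolled in the PATH arm | 10.2 |
| Alpha, sidedness | not stated for acceptability; two-sided 0.05 in the preceding sentence; two-sided 0.2 for Aim 2 | 10.2, 10.1 |

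**Trying to reproduce 95%, with 1.8 as the SD between participants**

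Standardised effect: d = (7.8 − 7.0)/1.8 = 0.444.

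One-sample t-test: power = P(T > t_crit), where T is noncentral t with n − 1 degrees of freedom and noncentrality d√n. For n = 30 the noncentrality is 0.444 × √30 = 2.43. The critical values at alpha 0.05 are 2.045 two-sided and 1.699 one-sided.

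| n | Alpha | Two-sided | One-sided |
|---|---|---|---|
| 30 | 0.05 | 65.3% | 76.8% |
| 35 | 0.05 | 72.4% | 82.4% |
| 30 | 0.20 | 86.8% | 94.3% |

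The normal approximation at n = 30, alpha 0.05, gives Φ(2.434 − 1.960) = 68.2% two-sided and Φ(2.434 − 1.645) = 78.5% one-sided.

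The nearest value to 95% at n = 30 comes from one-sided alpha 0.20. The plan states that nowhere; its 0.2 level is two-sided and belongs to Aim 2. Counting both arms (n = 70) gives 95.6% two-sided at 0.05, but usual-care participants do no exercises and rate none.

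**A bare threshold on the observed mean**

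P(observed mean ≥ 7.0) = Φ(0.8 × √30 / 1.8) = Φ(2.43) = 99.3%. This is not 95% either.

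**What 95% would need at alpha 0.05**

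- n = 68 two-sided or 57 one-sided, with 7.8 ± 1.8 kept; or
- at n = 30, a true mean of 8.23 two-sided or 8.11 one-sided; or
- at n = 30, an SD of 1.17 two-sided or 1.30 one-sided.

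**The other figures in the same paragraph**

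Feasibility, 80% against 50%, n = 30, two-sided 0.05: Φ[(0.30 × √30 − 1.96 × 0.5)/0.4] = 95.1% (93.9% by the exact test). The between-group effect of 0.74 with 30 per group has 80.5% power. Both agree with the plan, so the same convention works for the neighbouring figures and fails only for acceptability.

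**If 1.8 is the SD of a single rating**

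Averaging nine ratings with within-person correlation ρ gives an SD of 1.8 × √[(1 + 8ρ)/9] for a participant's mean. This is an assumption range, because the plan gives no ρ.

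| ρ | SD of participant mean | Power, two-sided 0.05, n = 30 |
|---|---|---|
| 0.30 | 1.11 | 96.9% |
| 0.35 | 1.17 | 95.2% |
| 0.50 | 1.34 | 88.4% |
| 0.60 | 1.44 | 83.4% |

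Power reaches 95% for ρ up to about 0.35 two-sided or 0.46 one-sided.

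**The two rules**

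Suppose eight exercises have a combined ease and utility mean of 7.8 and one has 6.9, with equal numbers rating each. The overall mean is (8 × 7.8 + 6.9)/9 = 7.7. That passes a rule on one combined mean and fails a rule on each exercise. This only illustrates that the rules can disagree. The documents do not allow the likelihood of that to be estimated.

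**The case against.** Four points can be made for the plan.

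1. **The unit of 1.8 is open.** Ratings are collected after each exercise, so 1.8 may describe single ratings, and 95% could then be correct. This stands as a limit on the replacement figure. It does not rescue the statement, because the correlation it needs appears nowhere. It also cuts the other way: 65% and 77% rest on an assumed t-test, alpha 0.05 and a per-participant SD. Those are, however, the ordinary reading of a mean ± SD and the alpha of the sentence before, and they are declared here.
2. **No test is planned.** Section 10.1 only compares a mean with 7.0, and on the per-participant reading an observed mean clears that threshold 99.3% of the time. This is right, and the shortfall in power must not be read as a 35% chance of missing an acceptable programme. It also means that the power claim is attached to no stated analysis.
3. **The sample size does not depend on this figure.** Correct; it is set by expected completers and feasibility.
4. **Section 10.1 does not expressly say that its combined score is pooled over exercises.** It might mean ease and utility combined within each exercise. This stands as an ambiguity. A single combined score, set after a sentence that distinguishes each exercise from overall, is more naturally read as one overall figure. On either reading the two sections are worded differently and need one rule.

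**Conclusion.** Both parts hold.

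The stated 95% cannot be obtained from the inputs given. With 1.8 as the SD between participants, 30 raters and alpha 0.05, power is about 65% two-sided or 77% one-sided, a shortfall of 30 or 18 percentage points. No design that the plan states gives 95% on that reading. Confidence that the figure does not follow is high. Confidence in the replacement is moderate, because the unit of the SD is not stated. The prior figure also covers utility alone, whereas the acceptability criterion includes ease.

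The acceptability rule for a primary endpoint is stated in two forms that can give opposite answers on the same data.

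The sample size and the conduct of the trial are unaffected. This should be fixed before analysis.

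**What to change.** **Section 10.2.** Do one of the following:

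- Replace 95% with the figure that follows from the stated inputs (about 65% two-sided or 77% one-sided at alpha 0.05, n = 30, if 1.8 is confirmed as the SD between participants), and name the test, alpha, sidedness and SD basis.
- If acceptability is only a threshold on the observed mean, delete the power claim and say that the mean will be reported with its 95% confidence interval. The expected half-width is 2.045 × 1.8/√30 = 0.67 points at n = 30.
- If 95% came from other inputs, such as a per-rating SD with an assumed correlation, state them.

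**Sections 1.2 and 10.1.** State one acceptability rule in identical words, fixed before analysis. It should say whether the threshold applies to each exercise or overall, and whether ease and utility are averaged or must each reach 7. One workable choice is the overall mean combined score of at least 7.0, with the per-exercise means reported descriptively. The choice is the sponsor's.

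**Cost.** Wording in three sections, with no change to sample size, data collection or conduct.

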10.3. Data security

Participant data will be collected using REDCap. We will maintain a separate list of participant names and study IDs, which will be saved in password-protected files. Participants will be identified on study forms by case number only to protect confidentiality. Identifiers such as names will only be used during the initial data retrieval process and can be destroyed once all data records have been obtained and data analysis has been completed as discussed previously.

Participants' responses to survey questions will remain confidential unless there is active suicidal ideation confirmed by the research team. Under these circumstances, as clearly stated in the participant

PROTOCOL TITLE: Randomized Trial of a Positive Psychology Intervention for Patients with Hematologic Malignancies Undergoing Hematopoietic Stem Cell Transplantation

consent form, the study CRC will inform the PI who will determine the need to involve social work, psychiatry and/or take further action as deemed necessary.

We will ensure that contact with participants is confidential by using only the phone numbers and other contact information that are specifically allowed by the participants and not leaving study-related messages for participants unless expressly allowed by participants. Upon enrollment, we ask all participants if it is acceptable to leave voice messages on their phones, as well as the appropriate times to call them. We will adhere to all participant requests regarding contact.

In addition, as stated previously, all study staff will undergo an extensive training on study procedures as well as data management to ensure data security and maintaining of confidentiality.

10.4. Quality control for collected data:

Our study staff will utilize double-data entry for approximately 10% of the data entered through REDCap to ensure high data quality. A research coordinator, blinded to the study intervention, will double enter 10% of the data through REDCap to check on data fidelity. If an error is found, the research coordinator will double enter an additional 5% of the data through REDCap. This process will continue until no errors are found. Also, the research coordinator will perform 'test downloads' of the data to ensure that it can be captured in the statistical package to be used in this study.

11.0 Provisions to Monitor the Data to Ensure the Safety of Subjects*

Purpose of Data and Safety Monitoring Plan:

The purpose of the data and safety monitoring plan is to establish standards that will ensure that this protocol complies with Federal Regulations, Health Insurance Portability and Accountability Act (HIPAA) requirements and applicable Dana Farber Harvard Cancer Center (DF/HCC) Standard Operating Procedures.

General Roles and Responsibilities:

The PI ([name]) will work closely with Drs. [name] (mentor) and [name] (mentor), who have extensive expertise conducting randomized supportive care trials to ensure the successful implementation of the proposed project. [name] will be responsible for all aspects of conducting the protocol, which includes:

- Overseeing the development, submission, and approval of the protocol as well as subsequent amendments.
- Ensuring that the research team members are qualified and appropriately resourced to conduct the protocol.
- Following the procedures as outlined in this Data and Safety Monitoring Plan. Detail plan is also in (Appendix X).

PROTOCOL TITLE: Randomized Trial of a Positive Psychology Intervention for Patients with Hematologic Malignancies Undergoing Hematopoietic Stem Cell Transplantation

- Training the clinical research coordinators prior to enrolling participants and throughout the trial's conduct as needed.
- Monitoring the progress and overall conduct of the study.
- Reviewing data collection and entry and maintaining timely submission of data for study analysis.
- Ensuring compliance with all requirements as set forth in the Code of Federal Regulations, Dana Farber Harvard Cancer Center requirements, HIPAA requirements, and the approved protocol.
- Committing to provisions that the protocol will not be rewritten or modified by anyone other than the overall PI.
- Monitoring accrual and address concerns if accrual goals are not met.

The Dana-Farber Cancer Center is expected to comply with all applicable federal regulations and requirements, the protocol and HIPAA requirements. Specifically, it will be responsible for:

- Reviewing registration materials for eligibility and registering participants with the DF/HCC Quality Assurance for Clinical Trials (QACT).
- Overseeing the data collection process.
- Maintaining documentation of Serious Adverse Events (SAE) reports and deviations/violations.
- Maintaining regulatory documents which include but not limited to the following: IRB approvals/notifications, confirmation of Federal wise Assurances (FWAs), all SAE submissions, screening logs, IRB approved consents.
- Conducting regular communications with overall PI and maintain documentation of all relevant communications.
- Documenting the delegation of research specific activities to study personnel.
- Maintaining regulatory files.
- Having office space, office equipment, and internet access that meet HIPAA standards.
- Participating in quality assurance activities and meet with monitors or auditors at the conclusion of a visit to review findings.
- Providing follow-up and/or corrective action plans for any monitoring queries or audit findings.

Intervention Training and Supervision:

- **Study Staff Training:** We will conduct a full day training for the clinical research coordinator (CRC) to ensure consistent recruitment and enrollment procedures. We will train the CRC to: 1) identify potentially eligible patients via the transplant clinic schedule and/or database; 2) track potentially eligible patients; 3) communicate with the treating clinicians about patient eligibility; 4) obtain informed consent from patients; and 5) monitor participants longitudinally and administer study questionnaires. In addition, [name] will meet with the CRC weekly to address any study issues or concerns. Drs. [name] and [name] will join these weekly meetings as needed.
- **Assessment of Intervention Fidelity:** To ensure the appropriate delivery of the intervention, 10% of all intervention calls will be recorded and reviewed with the research mentorship team (Drs. [name] and [name]). The research mentorship team will review recorded intervention sessions for consistency with explanation and delivery of positive psychology exercises. These measures will also provide accurate data on intervention feasibility. The research mentorship team will also discuss any issues or concerns regarding the intervention fidelity.

PROTOCOL TITLE: Randomized Trial of a Positive Psychology Intervention for Patients with Hematologic Malignancies Undergoing Hematopoietic Stem Cell Transplantation

Informed Consent Requirements:

The Dana Farber Harvard Cancer Center approved informed consent document will serve as a template for the informed consent.

Protocol Confidentiality: All documents, investigative reports, or information relating to study participants will be kept strictly confidential. We will ensure confidentiality is maintained by identifying participants on all study materials only by participant number, visit number, and date of visit. By recording study data in this manner, all information will be considered 'de-identified,' and therefore compliant with the Standards for Privacy of Individually Identifiable Health Information ("Privacy Rule") of the Health Insurance Portability Act of 1996. We will keep participant data in a computer file that is password protected. Only [name] and research team will have access to the data. We will maintain a link between the participant name and study number in a separate password protected file.

Data Management Organizational Structure: [name] and the CRC will develop the study specific database to ensure all data is entered appropriately. The CRC will routinely evaluate the data and discuss any problems and questions with [name] at a weekly meeting. Data management formal reports on record status across the three following domains will be employed: entered, verified, and edited. These reports of data records will be evaluated once a month during the final team meeting of the month. To help ensure data protection, backup copies, automatically generated by our computer systems, will be available.

Attrition Safeguards/Protection of Loss of Data:

A notable methodological consideration pertaining to the proposed research is protection against attrition. Our research group has conducted numerous clinical intervention studies. In our previous work, we have learned that individuals are best retained in studies when there is 1) a familiarity with study personnel (e.g., ability to effectively establish rapport), 2) team-based persistence in conducting follow-up assessments, and 3) intervention sessions happening in tandem with ongoing medical appointments or inpatient hospitalizations. Yet, it is worth noting here a number of key issues that we have thoughtfully considered in the construction of the present proposal related to attrition. Attrition in clinical research studies overall occurs from three major sources: (a) disease worsening/mortality, (b) refusal to participate, and (c) loss of contact.

- **Disease Worsening/Mortality:** Given the burden of treatment for patients with hematologic malignancies undergoing HSCT, we do anticipate that a minority of participants will be unable to complete the study protocol due to deteriorating health or death. Our research team has given considerable thought to this concern and adequately powered the study to account for missing data. Based on prior work, we anticipate a 15% attrition rate. The study CRCs will maintain detailed records for patient attrition due to disease-related factors.
- **Refusal to Participate:** Participants who are successfully recruited into the study but later refuse to participate in subsequent intervention sessions pose a threat to the proposed study. In our previous trial, our refusal to participate rate after study enrollment was quite low and all participants who started the intervention actually completed the all the intervention sessions. Again, the CRCs will maintain detailed records for patient refusals.
- **Loss of Contact:** Another source of attrition involves those subjects who are successfully recruited into the study but who cannot be located for subsequent follow-up assessments. Like attrition due to subject refusal, attrition due to loss of contact poses a threat to the proposed study. We do not anticipate this to be a major

PROTOCOL TITLE: Randomized Trial of a Positive Psychology Intervention for Patients with Hematologic Malignancies Undergoing Hematopoietic Stem Cell Transplantation

issue for the proposed study given the intensive and frequent outpatient follow-up visits for patients with hematologic malignancies during the first six months post-HSCT.

- Participant Adherence: To minimize attrition, we plan to use multiple strategies to reduce drop-out. Potential participants will be invited to participate in the baseline assessment during which time participants will receive a thorough explanation of the study treatments, requirements, and follow-up procedures. Study staff will emphasize the patient's responsibility as a research participant, reiterate confidentiality, and work to develop good rapport. We will make a concerted and systematic effort to facilitate adherence to the completion of follow-up assessments. This task will be accomplished by: (1) obtaining longitudinal participant-reported measures during regular follow-up appointments; (2) providing participants with remote access to complete the longitudinal study measures; and (3) making reminder phone calls and administering the study measures over the phone if necessary for participants who do not have appointments in the window for assessment completion.

Data Safety and Monitoring Plan

The following procedures will be followed, in compliance with NIH requirements, to ensure the safety of study participants and the validity and integrity of data.

- Range of Safety Reporting: [name] will review all data pertaining to safety during the weekly research team meeting. These include adverse events (AEs) and serious adverse events (SAEs), but also other data that may reflect differences in safety such as treatment retention rates and reasons for dropout.
- Data Repository: [name] will oversee all aspects of data collection for the study and the CRCs will have the operational responsibility of data management. Specifically, the research team will develop a study specific data management protocol and standard operating procedures for the creation and testing of all study forms, data collection, quality control, and data extraction. These forms will be standardized. We will provide ongoing oversight of data management throughout the study, and will be responsible for generating reports and datasets for quality control and data analysis. All data management activities will utilize REDCap, a software toolset and workflow methodology for electronic collection and management of research and clinical trial data. REDCap data collection projects rely on a thorough study-specific data dictionary defined in an iterative self-documenting process by all members of the research team with planning assistance from Partners HealthCare Research Computing, Enterprise Research Infrastructure & Services (ERIS) group. REDCap provides secure, HIPAA compliant, web-based applications with an intuitive interface for users to enter data and have real time validation rules (with automated data type and range checks) at the time of entry.
- Serious Adverse Events: Expedited review will occur for all events meeting the FDA definition of a SAE (i.e., any fatal event, immediately life-threatening event, permanently or substantially disabling event, event requiring or prolonging inpatient hospitalization, or any congenital anomaly). This also includes any event that a study investigator judges to impose a significant hazard, contraindication, side effect, or precaution. Given that this is a supportive care study in a population at risk for disease relapse and death due to transplant complications (unrelated to the study procedures), only SAEs that may potentially be related to the study will be reported to the IRB. All relevant information will be reported to the IRB for each SAE including information about the event and its outcome, study condition, concomitant medications, the subject's medical history and current conditions, and all relevant laboratory data. Notification by secure e-mail of all related study forms shall be made to the IRB within 24 hours of the occurrence of any SAE that might be relevant to the study. Information

PROTOCOL TITLE: Randomized Trial of a Positive Psychology Intervention for Patients with Hematologic Malignancies Undergoing Hematopoietic Stem Cell Transplantation

will be reviewed and a determination made of whether there was any possible relevance to the study interventions. Additional reporting to the NIH will be made according to their respective regulations governing SAE reporting.

- **Non-Serious Adverse Events:** The research team will review monthly summary reports of the numbers and rates of adverse events by treatment group. These reports will include types of events, severity, and treatment phase.
- **Other Safety-Related Reports:** The research team will review weekly summary reports of treatment retention and reasons for dropout, by treatment group.

Monitoring of Data Quality by the research team:

The research team will review the following items on weekly basis to ensure data quality and completeness:

- Total enrollment compared with anticipated enrollment
- Number of ineligible patients registered
- Proportion of missing participant-reported outcomes
- Proportion of other missing data
- Number of participants lost to follow-up
- Number of participants completing the study

Additionally, the research team will receive a report on safety and outcome data for the trial:

- Number of deaths, listed by cause
- Number and types of SAEs
- Number and types of reportable AEs
- Number of participants with primary outcomes
- Number of participants with secondary outcomes

ClinicalTrials.gov Requirements

As per Public Law 110-85, this is an applicable clinical trial and will be registered and results will be reported with ClinicalTrials.gov. The CRC will be responsible for handling ClinicalTrials.gov requirement for this project under [name] (PI) oversight. She will work closely with the Partners Human Research Affairs QI Program to register the trial prior to enrolling the first subject. Once a record is established, she will confirm accuracy of record content; resolve problems; and maintain records including content update and modification. She will also be responsible for aggregate results reporting and AE reporting at the conclusion of the project. We will ensure that summary results will be reported to clinicaltrials.gov no later than one year after the primary completion date.

